#### **Treatment Phase (Cycle 1 [Induction] and Cycles 2 and 3 [Consolidation])**

Assessments should be collected on the day and time period required as per the schedule of assessments ([Appendix 1](#)).

If the specified screening assessments found in [Appendix 1](#) are performed up to 72 hours prior to Cycle 1, Day 1, these assessments do not have to be repeated on Cycle 1, Day 1 except for hematology and biochemistry, which must be performed 1 day prior to Cycle 1, Day 1. Note: Hematology assessments should be obtained and checked PRIOR to randomization.

At the end of each cycle, the response to treatment will be determined. Patients in CRp/CRi by Day 28 will be allowed a maximum of an additional 28 days (until Day 56) for blood counts to recover before proceeding with consolidation therapy. The end of cycle is hence defined as either Day 28 or the day of the best peripheral blood count recovery, up until Day 56.

Please see [Appendix 1](#) and [Appendix 4](#) for detailed instructions on bone marrow collection and HMRA assessment during the treatment phase.

Note that the *futility* interim analysis will include a comparison of the proportion of confirmed CR/CRp between study arms (see Section [3.4.1](#)). For patients proceeding to Cycle 2, the best response at the end of Cycle 2 will be used as the confirmed response. For patients not proceeding to Cycle 2, the response observed at the end of Cycle 1 must be confirmed 30 days ( $\pm 3$  days) later.

Sampling timepoints for bone marrow aspirate and/or blood for HMRA are outlined in [Appendix 1](#).

## Study Drug Completion/Discontinuation Visit

Once a patient completes study treatment or discontinues study drug for any reason, the Study Drug Completion/Discontinuation eCRF page must be completed. To allow for this, patients will be asked to return to the clinic 28 days (+28 day window) after the last dose of study medication is administered.

In the event that the decision to withdraw from further therapy on the study occurs after 28 days from the last dose of idasanutlin/placebo (e.g., due to an interruption of an intended cycle continuation due to an adverse event), then the study drug discontinuation visit should occur on the date of withdrawal.

For a patient in remission after induction who is not continuing on to consolidation after the allowed recovery period for blood counts (up until Day 56), the study drug completion/discontinuation visit and the confirmatory response assessment visit may occur during the same time window. Please consult [Appendix 1](#) for guidance on data entry into the eCRF in this scenario.

## Follow-Up

Patients in CR/CRp/CRi after terminating study treatment will be followed for EFS, *DOR*, and *LFS*. HMRA will be performed monthly ( $\pm 5$  days) until disease progression/relapse is noted or until the patient moves to HSCT. Every 3 months HMRA will include assessment of bone marrow aspirate; in all other instances, HMRA will be based on peripheral blood counts only.

In the event of relapse, a HMRA based on a bone marrow aspirate is required. In addition, whole blood in EDTA for biomarker analysis should be obtained.

For patients who move to HSCT, an HMRA based on a bone marrow aspirate should be performed to document the bone marrow status prior to the start of conditioning therapy. The quantity of the bone marrow aspirate should also allow for exploratory biomarker analyses (MRD/Flow, EDTA, and Paxgene), and the hematopoietic cell transplantation-specific comorbidity index (HCT-CI) score (Sorrer et al. 2005; Sorror 2013) should be obtained to document the patient's health status prior to the start of conditioning therapy.

All patients will be followed every 3 months for study treatment-related serious adverse events, fatal adverse events, subsequent anti-cancer therapies, and survival status. Survival follow-up ends with death or end of study. Adverse events should be followed as outlined in Section 5.3.1 and Section 5.6. Please see [Appendix 1](#) for the schedule of follow-up assessments.

### **4.5.3 Hematopoietic Stem Cell Transplant**

For patients who proceed to undergo HSCT after completion/discontinuation of study medication, data regarding the health status (HCT-CI score [[Appendix 15](#)]), leukemia status (HMRA) within 28 days prior to start of conditioning, date of transplant, type of transplant (allogeneic versus autologous, peripheral blood versus bone marrow versus cord blood, matched sibling versus matched unrelated donor, or mismatched donor or haploidentical donor), and conditioning (myeloablative versus reduced) will be collected. Information on engraftment status and survival will be requested every 3 months. Note: Donor lymphocyte infusion is allowed under this protocol and should be recorded in the eCRF as an anti-cancer therapy.

### **4.5.4 Medical History and Demographic Data**

Medical history includes clinically significant diseases within the last 5 years, surgeries, AML cancer history (including prior cancer therapies and procedures, cytogenetics, and leukemia markers) and all medications (e.g., prescription drugs, over-the-counter drugs, herbal or homeopathic remedies, nutritional supplements) used by the patient within 28 days prior to the screening visit.

Demographic data will include age, sex, and self-reported race/ethnicity.

### **4.5.5 Physical Examinations**

A complete physical examination should include an evaluation of the head, eyes, ears, nose, and throat, and the cardiovascular, dermatological, musculoskeletal, respiratory, GI, genitourinary, and neurological systems. Any abnormality identified at baseline should be recorded on the General Medical History and Baseline Conditions eCRF.

At subsequent visits (or as clinically indicated), limited, symptom-directed physical examinations should be performed. Changes from baseline abnormalities should be recorded in patient notes. New or worsened clinically significant abnormalities should be recorded as adverse events on the Adverse Event eCRF.

### **4.5.6 Performance Status**

Performance status will be measured using the ECOG performance status at baseline and will be assessed at regular intervals throughout the study. Further details can be found in [Appendix 12](#).

### **4.5.7 Vital Signs**

Vital signs will include measurements of respiratory rate, pulse rate, and systolic and diastolic blood pressure while the patient is in a seated position, BSA, and body temperature (°C). Weight will be recorded at screening and as indicated in [Appendix 1](#). Height will be recorded only at screening.

#### 4.5.8 Hematologic Malignancy Response Assessment

The following criteria should be used to determine hematologic malignancy response (Cheson et al. 2003; Döhner et al 2017; NCCN guidelines):

- CR: Bone marrow blasts < 5%, absence of blasts with Auer rods; absence of extramedullary disease; ANC  $\geq 1.0 \times 10^9/L$ ; platelets  $\geq 100.0 \times 10^9/L$
- CRi: All CR criteria except for residual neutropenia (ANC <  $1.0 \times 10^9/L$ ) or thrombocytopenia (platelets <  $100.0 \times 10^9/L$ )
- CRp: All CR criteria except for thrombocytopenia (platelets <  $100.0 \times 10^9/L$ )
- Treatment failure:
  - Resistant disease:  
Failure to achieve CR, CRi, or CRp; only includes patients surviving  $\geq 7$  days following completion of initial treatment, with evidence of persistent leukemia by blood and/or bone marrow examination.
  - PR and SD/hematologic improvement (HI) will be considered treatment failure.
    - PR  $\geq 50\%$  decrease in bone marrow blasts
    - SD/HI = decreased peripheral blast percentage, decreased frequency of transfusions, improvement in peripheral cell counts
  - Death in aplasia:  
Deaths occurring  $\geq 7$  days following completion of initial treatment while cytopenic; with an aplastic or hypoplastic bone marrow obtained within 7 days of death, without evidence of persistent leukemia
  - Deaths from indeterminate cause:  
Deaths occurring before completion of therapy, or < 7 days following its completion; or deaths occurring  $\geq 7$  days following completion of initial therapy with no blasts in the blood, but no bone marrow examination available
- Relapse of Disease:  $\geq 5\%$  bone marrow blasts; or reappearance of blasts in the blood, or development of extramedullary disease.

HMRAs require sampling of blood and bone marrow as indicated. Bone marrow aspirates are required, but if bone marrow biopsies are performed, the biopsy results should be provided. Depending on timepoint in the schedule of assessments the HMRA is established based on blood counts only, or includes the assessment of bone marrow. Patients will be considered to be in their best response state until definitive evidence of relapse is available from blood counts, bone marrow aspirate, or bone marrow biopsy.

In the event that a bone marrow aspirate or biopsy is equivocal (i.e., a recovering marrow), the bone marrow assessment and complete blood count should be repeated > 7 days later.

In case disease progression/relapse is determined solely by symptomatic deterioration or by a hematology assessment, a bone marrow aspirate should be performed at that

time to complete HMRA. If a patient progresses/relapses outside of the scheduled visit, an unscheduled HMRA must be provided.

If a bone marrow aspirate is performed at any unscheduled timepoint while on study, an unscheduled HMRA must be provided.

Please note that at the time of bone marrow sampling for HMRA the bone marrow sample collected (aspirate) should also allow for exploratory analyses (MRD by flow cytometry, EDTA, Paxgene) and amount taken should be taken into consideration (Section 4.5.10.6).

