- For patients remaining in CRi until Day 42 weekly blood counts should be obtained up to Day 56. As soon as blood counts recovered and CR, CRp or CRi with ANC  $\geq 0.5 \times 10^9/L$  is observed (but latest at Day 56), patients may start Cycle 2 with 50% idasanutlin (300 mg QD in the morning) and 50% cytarabine (0.5 g/m^2). Once the cytarabine dose is reduced, the dose reduction should be maintained for the remainder of the cycles.

For more detailed instructions on continuation of study medication based on response criteria see [Appendix 4](#). For guidelines on mandatory and recommended prophylaxis regimens, consult [Appendix 14](#).

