### **Throughout the Study**

During the treatment period, HMRAs are to be performed and reviewed before the start of a new treatment cycle. In the event that a patient has a dosing delay > 7 days, weekly blood counts must be performed for HMRA to document evidence of non-progression. Treatment failure and relapse will lead to discontinuation of the study medication (See [Appendix 1](#), [Appendix 3](#), and [Appendix 4](#) for further details).

Bone marrow and blood will be required for HMRA after Cycle 1 for all patients. Depending on blood count recovery, this will be between Day 28 and Day 56 latest. Patients with CR or CRp by Day 42 may proceed with Cycle 2 (50% idasanutlin [300 mg QD in the morning], 100% cytarabine [1 g/m^2]). Patients remaining in CRi up to Day 42 will need to undergo another HMRA to determine response status. Based on this, patients with CR, CRp, or CRi with ANC  $\geq 0.5 \times 10^9/L$  may continue with Cycle 2 (50% idasanutlin [300 mg QD in the morning], 50% cytarabine [0.5 g/m^2]). Once the cytarabine dose is reduced, the dose reduction should be maintained for the remaining cycles. With respect to continuation with Cycle 3 different criteria apply before and after the *futility* interim analysis (please see below). Refer to the schedule of assessments ([Appendix 1](#)) and the treatment algorithm ([Appendix 4](#)) for further details.

During the follow-up of patients who remain in CR, CRp, or CRi after treatment, blood will be required every month and a bone marrow aspirate will be required every 3 months to allow for HMRA until relapse or HSCT. Refer to [Appendix 1](#) and [Appendix 3](#) for further details.

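### The CRi definition contains the CRp definition, while the Cycle 2 cytarabine instruction for low platelets persisting to Day 42 depends on which label is used

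*Protocol*

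**What the plan says.** **Definitions (Protocol 4.5.8).** CR requires, besides the marrow and extramedullary criteria, ANC of at least 1.0 and platelets of at least 100 × 10⁹/L. The CRi entry opens "CRi: All CR criteria except for residual neutropenia" (ANC below 1.0) and continues with the alternative "or thrombocytopenia (platelets", where the bracket gives the limit as below 100 × 10⁹/L. The CRp entry reads "CRp: All CR criteria except for thrombocytopenia", with the same platelet limit.

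**Cycle 2 instructions.** Protocol 4.5.8, under Throughout the Study, says "Patients with CR or CRp by Day 42 may proceed with Cycle 2 (50% idasanutlin [300 mg QD in the morning], 100% cytarabine" at 1 g/m². It then says "Patients remaining in CRi up to Day 42 will need to undergo another HMRA to determine response status". After that assessment, patients in CR, CRp, or CRi with ANC of at least 0.5 × 10⁹/L "may continue with Cycle 2 (50% idasanutlin [300 mg QD in the morning], 50% cytarabine" at 0.5 g/m², and the reduction is kept for the remaining cycles. Section 4.3.2.4 makes the same split: CR or CRp observed no later than Day 42 goes with 100% cytarabine, whereas "For patients remaining in CRi until Day 42 weekly blood counts should be obtained up to Day 56", followed by 50% cytarabine. The idasanutlin/placebo dose is the same on both routes.

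**Analysis.** SAP 4.4.2 tabulates CR, CRp and CRi as separate categories and refers to Protocol 4.5.8 for the criteria. SAP 4.11.1 defines confirmed CR, for the futility analysis, as CR or CRp lasting at least 28 days.

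**The concern.** Two response labels that carry different instructions should not both fit the same blood counts. Here one pattern, recovered neutrophils with low platelets, fits both. Two sites following 4.5.8 word for word could code identical patients differently, and would then be directed to different cytarabine doses and different start windows for Cycle 2. The split between CRp and CRi in the response table, and the cumulative-dose, dose-intensity and dose-modification summaries (SAP 4.7.1), would then partly reflect site coding habits as well as the patients' recovery.

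**Working it through.** The plan gives no figure to reproduce. The check sets the definitions against the dosing rules.

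**Step 1. Labels by blood count**, for a patient who meets the marrow criteria and has no extramedullary disease (counts × 10⁹/L, definitions from Protocol 4.5.8):

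| | ANC | Platelets | CR | CRp | CRi |
|---|---|---|---|---|---|
| 1 | ≥ 1.0 | ≥ 100 | yes | no | no |
| 2 | < 1.0 | ≥ 100 | no | no | yes |
| 3 | < 1.0 | < 100 | no | no | yes, if the or is inclusive |
| 4 | ≥ 1.0 | < 100 | no | yes | yes |

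Only row 4 has two labels. The overlap does not depend on how the or is read: an exclusive or would remove row 3 from CRi but leave row 4 in both. As written, every CRp patient is also a CRi patient.

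**Step 2. What the label leads to when row 4 persists to Day 42** (Protocol 4.3.2.4 and 4.5.8), assuming five dosing days and no other modification:

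| | Label CRp | Label CRi |
|---|---|---|
| Cycle 2 start | by Day 42 | after a further HMRA, up to Day 56 |
| Cytarabine per cycle | 1 g/m² × 5 = 5 g/m² | 0.5 g/m² × 5 = 2.5 g/m² |
| Cycles 2 and 3 together | 2 × 5 = 10 g/m² | 2 × 2.5 = 5 g/m² |

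The dose ratio is 10 / 5 = 2, and the latest start differs by 56 − 42 = 14 days.

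**Step 3. Where the conflict stops.** If platelets reach 100 × 10⁹/L by Day 42, the patient is in CR and the instruction is 100% whatever label was used before. Once a patient is on the route after Day 42, CR, CRp and CRi with ANC of at least 0.5 all go with 50%, so the label no longer matters. Patients who do not enter Cycle 2 are not affected by the dose rule.

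**Step 4. Is there a tie-break?** The best-response-state sentence in Protocol 4.5.8 governs how long a response is held; it does not rank CRp against CRi. SAP 4.4.2 lists CRp before CRi and takes the best assessment over Cycle 1, but states no precedence. Protocol 5.1.2.5 sends the reader to the dosing guidelines by blood count in Appendix 4. Those decision trees are figures that could not be seen here.

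**Step 5. Which analyses use the label?** By the definitions in SAP 2.2:

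- Final CR is CR only.
- ORR and LFS pool CR, CRp and CRi.
- EFS failure is failure to achieve CR.
- DOR and the HSCT proportion follow CR.

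None of these turns on CRp versus CRi. OS is touched only through the treatment received. The label does enter the response-category table and, through the dose given, the exposure and dose-modification summaries. An optional exploratory comparison by level of response (SAP 4.9) would inherit the coding if it separates the two.

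**The case against.** The strongest reply is that the documents already point to one label.

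- Coding isolated thrombocytopenia as CRi would leave CRp empty, yet CRp is used as a separate category throughout.
- The neutrophil condition is attached only to CRi in 4.3.2.4 and 4.5.8, as if CRi were the category with unrecovered neutrophils.
- SAP 4.4.2 takes the best response and lists CRp ahead of CRi.
- In the Phase I combination data (Protocol 1.2.1.1), CR/CRp was 21 of 75 and adding CRi gave 22 of 75, so CRi contributed one patient as its own category.
- Appendix 4, to which dosing is deferred, may resolve the case by blood count.

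As evidence of intent this stands: CRp was probably meant for isolated thrombocytopenia. It does not amount to a rule. A patient with ANC of at least 1.0 satisfies the CRi neutrophil condition automatically, so that condition is compatible with either label, and a site that codes CRi from 4.5.8 is following the text. If Appendix 4 does settle the matter, 4.5.8 should still agree with it.

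Three stronger readings are tempting and are not supported:

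- **Every responder with low platelets is affected.** The dose conflict needs entry into Cycle 2 with isolated thrombocytopenia still present at Day 42.
- **Isolated thrombocytopenia is the pattern to expect with this drug.** Protocol 4.4.2.3 does warn of long-lasting thrombocytopenia, but 5.1.1.2 reports the same mean recovery time of 34 days for platelets and leukocytes, and 1.2.1.2 names both thrombocytopenia and neutropenia as dose limiting. No frequency of the isolated pattern is given.
- **The efficacy conclusions are at risk through confirmed CR.** That definition counts CRp but not CRi, so the label could have moved a patient in the odds ratio compared with 2.0 and 2.5. It was used only in the futility analysis, which was non-binding and, by SAP 4.11.1 and the note to SAP Appendix 2, is already complete.

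**Conclusion.** The point holds within limits. As written, CRp lies wholly inside CRi, and for one blood-count pattern at Day 42 the two labels carry instructions that differ two-fold in cytarabine and by up to 14 days in the latest Cycle 2 start. This is a conflict between stated rules that must be reconciled; no view is taken on which label or dose is right.

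The number of patients concerned cannot be derived from the documents. A reader might infer that such a patient certainly qualifies for two doses under the whole protocol. That goes too far while the Appendix 4 trees are unseen, and the conclusion rests on the text of 4.3.2.4 and 4.5.8 alone. The remaining effect on the planned analyses is descriptive: the response-category table and the exposure and dose-modification summaries. Final CR, EFS, ORR, DOR, HSCT and LFS do not depend on the label.

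**What to change.** First check the Appendix 4 decision trees for a blood-count rule. Then reword Protocol 4.5.8 so that CRp and CRi are mutually exclusive, and reconcile 4.3.2.4, 4.5.8 and Appendix 4 so that each combination of ANC and platelets maps to one category and one dosing instruction. Issue matching eCRF completion guidance. The sponsor's clinical team decides which category and instruction apply.

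If some patients have already been coded, SAP 4.4.2 should say whether the category table uses the investigator's label or one derived from the recorded counts.

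The cost is a short protocol clarification and eCRF guidance. Sample size, alpha and the definitions of the efficacy endpoints do not change.

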### **Throughout the Study**

During the treatment period, HMRAs are to be performed and reviewed before the start of a new treatment cycle. In the event that a patient has a dosing delay > 7 days, weekly blood counts must be performed for HMRA to document evidence of non-progression. Treatment failure and relapse will lead to discontinuation of the study medication (See [Appendix 1](#), [Appendix 3](#), and [Appendix 4](#) for further details).

Bone marrow and blood will be required for HMRA after Cycle 1 for all patients. Depending on blood count recovery, this will be between Day 28 and Day 56 latest. Patients with CR or CRp by Day 42 may proceed with Cycle 2 (50% idasanutlin [300 mg QD in the morning], 100% cytarabine [1 g/m^2]). Patients remaining in CRi up to Day 42 will need to undergo another HMRA to determine response status. Based on this, patients with CR, CRp, or CRi with ANC  $\geq 0.5 \times 10^9/L$  may continue with Cycle 2 (50% idasanutlin [300 mg QD in the morning], 50% cytarabine [0.5 g/m^2]). Once the cytarabine dose is reduced, the dose reduction should be maintained for the remaining cycles. With respect to continuation with Cycle 3 different criteria apply before and after the *futility* interim analysis (please see below). Refer to the schedule of assessments ([Appendix 1](#)) and the treatment algorithm ([Appendix 4](#)) for further details.

During the follow-up of patients who remain in CR, CRp, or CRi after treatment, blood will be required every month and a bone marrow aspirate will be required every 3 months to allow for HMRA until relapse or HSCT. Refer to [Appendix 1](#) and [Appendix 3](#) for further details.

### **Before *Futility* Interim Analysis**

The *futility* interim analysis will include a comparison of the proportion of confirmed CR or CRp between study arms. If a patient proceeds to Cycle 2, then the HMRA at the end of Cycle 2 (on Days 28–56 of Cycle 2) will be used as confirmation of response. If a patient does not receive a second cycle of therapy then the response from Cycle 1 should be confirmed 30 days ( $\pm 3$  days) later. In both cases confirmation of response requires bone marrow aspirate.

The decision criteria to continue with Cycle 3 are the same as applied in Cycle 1 for Cycle 2. Refer to the schedule of assessments ([Appendix 1](#)) and the treatment algorithm ([Appendix 4](#)) for further details.

### **After *Futility* Interim Analysis**

After the *futility* interim analysis bone marrow aspirate for confirmation of response is no longer required. However, HMRA including bone marrow assessment needs to be available for the last cycle received, that is, if a patient stops study medication after Cycle 2, then a HMRA including bone marrow aspirate is required; if a patient continues with Cycle 3 HMRA based on blood counts only is sufficient and HMRA based on bone marrow will be performed at the end of Cycle 3.

The decision to continue with Cycle 3 will no longer be based on bone marrow data, but on blood counts only. Refer to the schedule of assessments ([Appendix 1](#)) and the treatment algorithm ([Appendix 4](#)) for further details.

### **4.5.9 Laboratory Assessments**

Normal ranges for the study laboratory parameters must be submitted to Roche **BEFORE** the study starts.

Samples for the following laboratory tests will be sent to the study site's laboratory for analysis.

- Hematology (WBC count, RBC count, hemoglobin, hematocrit, platelet count, differential count [neutrophils, eosinophils, basophils, monocytes, lymphocytes, blasts, promyelocytes, myelocytes, metamyelocytes]). A manual differential (including WBC) may be needed if an automated differential does not provide blasts. Each differential should add up to 100% (or as close as possible).
- Biochemistry (glucose, urea or BUN, serum creatinine, creatinine clearance [at screening only determined by Cockcroft-Gault Formula], AST, ALT, LDH, alkaline phosphatase, total bilirubin (and direct bilirubin where total bilirubin > ULN), total protein, albumin, calcium, phosphorus, magnesium, sodium, potassium, bicarbonate, chloride, and uric acid)
- Urinalysis using standard dipstick assessment (pH, protein, glucose, blood, ketones, and leukocytes). This must be supplemented with laboratory quantification of any potentially relevant abnormalities as deemed necessary by the investigator.
- Serum pregnancy test in females of child bearing potential and postmenopausal females with less than 1 year of amenorrhea.
- Bone marrow aspirate (total cells counted, absolute mature neutrophils, mature eosinophils, mature basophils, monocytes, lymphocytes, blasts, promyelocytes, myelocytes, metamyelocytes, plasma cells, pronormoblasts, normoblasts, nucleated erythrocytes)
- Bone marrow biopsy (leukemia histology, cellularity, percent cellularity, percent blasts)

